7.2.4.1 Biomarker assessments in tumor tissue

7.2.4.1.1 Mandatory tumor sample collection

A mandatory newly acquired biopsy (preferred) or an archival specimen obtained at or since the time of diagnosis (within **3 months** prior to study treatment start is strongly recommended) must be provided during screening prior to the first dose of study treatment.

CNS and bone are excluded organs for biopsy and biomarker analyses.

For biomarker cohort only: A mandatory **newly acquired biopsy** specimen must be provided from cutaneous or subcutaneous lesions or nodal lesions during screening, at Cycle 1 Day 15 (+ 1 week window), 8-12 weeks after initiation of PDR001 therapy and at PD (at disease progression and/or at a subsequent disease progression per response criteria for immunotherapy if subject continues treatment post progression). If the newly acquired biopsy sample provided is determined to be insufficient for the proposed biomarker analyses, additional archival tumor tissue sample may be requested for the central BRAF V600 mutation confirmation.

All subjects will be required to provide a tumor tissue sample at screening prior to study treatment, as either a tumor block or a minimum of 25 FFPE slides. The minimum number of slides is indicated in order to have sufficient material for the central *BRAF* V600 mutation testing/confirmation [REDACTED] as described below:

- If local documentation of *BRAF* V600 mutation status is available, *BRAF* V600 mutation results will be subjected to retrospective central confirmation by a Novartis designated laboratory and FDA approved assay (e.g., Biomerieux THxID™-BRAF).
- In cases where an acceptable local result for *BRAF* V600 mutation is not available, a central test must be prospectively performed and the tumor sample should be sent to a Novartis designated central laboratory for testing by Day -20.

[REDACTED]

[REDACTED]

Tumor tissue collected (irrespective of the local and central *BRAF* V600 status) may be used for development of a potential future companion or complementary diagnostic assays.

In the biomarker cohort, additional mandatory newly acquired biopsies will be collected at Cycle 1 Day 15 (+7 day window), 8 – 12 weeks after initiation of PDR001 therapy and at PD (at disease progression and/or at a subsequent disease progression per response criteria for immunotherapy if subject continues treatment post progression). The samples will be used to assess the impact of dabrafenib, trametinib and PDR001 treatment on markers of the immune micro-environment. [REDACTED]

[REDACTED]

The biopsy at disease progression will be used to unveil potential mechanism/marker of resistance to the treatment. For these purposes, analysis similar to the ones described above

[REDACTED]

performed on the baseline and on treatment biopsies may also be performed on these samples. The goal of this analysis is to detect the presence of specific acquired somatic mutations or other genetic aberration that could account for acquired resistance to therapy, or to highlight changes in the neoantigenic potential of the tumor under the selective pressure of the treatment. These analyses may also be used to support development of future companion diagnostic tests.

7.2.4.1.2 Optional tumor sample collection

[figure not shown]

In addition to the mandatory tissue collection, newly acquired biopsies are requested upon signature of the relevant section of the ICF. CNS and bone are excluded organs for biopsy and biomarker analyses.

[figure not shown]
In the safety run-in and randomized cohort, an optional newly acquired tumor tissue can be collected at screening (unless sufficient tissue from a newly acquired biopsy was already provided for *BRAF* V600 central testing), on Cycle 1 day 15 (+ 7 day window) (Part 3 only), 8-12 weeks after initiation of PDR001 therapy and at PD (at disease progression and/or at a subsequent PD per response criteria for immunotherapy if subject continues treatment post progression).

In the biomarker cohort, an additional optional new tumor tissue may be collected during the course of the study depending on investigator assessment (e.g., responding/shrinking lesion needs to be collected prior to cycle 3).

[figure not shown]
7.2.4.2 Biomarker assessments in blood samples

7.2.4.2.7 Optional additional biomarkers assessments upon adverse event

If FFPE tissue is obtained as part of the evaluation of an AE that is suspected to be treatment-related (e.g., skin biopsy for rash), Novartis may request that remaining tissue to be submitted for central evaluation to gain further understanding of the AE, or other safety findings associated with that AE. For these reasons, additional analyses (similar to the ones described above for the baseline, on treatment and at disease progression biopsies) may be conducted on this material. In addition, an unscheduled blood sample collection may be requested in case of suspected adverse events and once the suspected adverse event is resolved.

7.2.5 Patient reported outcomes

The European Organization for Research and Treatment of Cancer's core quality of life questionnaire (EORTC-QLQ-C30, version 3.0), the EuroQoL 5-level instrument (EQ-5D-5L, tablet version), and the Melanoma Subscale of the Functional Assessment of Cancer Therapy–Melanoma (FACT-M) will be used to evaluate patient-reported outcome measures of health-related quality-of-life, functioning, disease symptoms, treatment-related side effects, and global health status. The EORTC QLQ-C30, EQ-5D-5L and Melanoma Subscale of the FACT-M are recognized as reliable and valid measures (Aronson 1993, Rabin 2001, Cormier 2008) frequently used in clinical trials of patients with advanced or metastatic cancer.

As per [Section 2.7](#), during a Public Health emergency as declared by Local or Regional authorities i.e. pandemic, epidemic or natural disaster, that limits or prevents on-site study visits, Clinical Outcomes Assessment (COA) data may be collected remotely (no longer applicable per protocol amendment 06).

Prior to the final PFS analysis:

All patient-reported outcomes (PRO) data will be collected using an electronic tablet device. All PRO assessments should be administered in the patients' local language according to the Visit Evaluation Schedule in [Table 7-3](#), prior to any tests, treatments or receipt of results from any test to avoid biasing the patient's perspective.

Patients should be given sufficient space and time to complete all study questionnaires and all administered questionnaires should be reviewed for completeness. If missing responses are noted, patients should be encouraged to complete any missing responses. Attempts should be made to collect responses to all questionnaires for all patients, including from those who discontinue prior to the study evaluation completion visit, however, if patients refuse to complete questionnaires, this should be documented in study source records. Patient's refusal to complete study questionnaires are not protocol deviations.

Completed questionnaires, including both responses to the questions and any unsolicited comments written by the patient, should be reviewed and assessed by the investigator before the clinical examination for responses which may indicate potential AEs or SAEs. This review should be documented in study source records.

[figure not shown]
If an AE or SAE is confirmed then the physician should record the event as instructed in [Section 8](#) of this protocol. Investigators should not encourage the patients to change responses reported in questionnaires.

Following primary PFS analysis

PRO data will no longer be collected and any additional data will not be analysed.

7.2.5.1 EORTC QLQ-C30

The EORTC QLQ-C30 contains 30 items and is composed of both multi-item scales and single-item measures. These include five functional scales (physical, role, emotional, cognitive and social functioning), three symptom scales (fatigue, nausea/vomiting, and pain), six single items

(dyspnea, insomnia, appetite loss, constipation, diarrhea and financial impact) and a global health status/QoL scale ([Aaronson 1993](#)).

All of the scales and single-item measures range in score from 0 to 100. A high scale score represents a higher response level. Thus, a high score for a functional scale represents a high / healthy level of functioning; a high score for the global health status / QoL represents a high QoL, but a high score for a symptom scale / item represents a high level of symptomatology / problems. All scoring will follow the scoring procedures defined by the EORTC Scoring Manual ([Fayers 2001](#)).

7.2.5.2 EQ-5D-5L

The EQ-5D-5L (tablet version) is a standardized measure of health utility that provides a single index value for one's health status. The EQ-5D-5L is frequently used for economic evaluations of health care and has been shown to be a valid and reliable instrument ([The EuroQol Group 1990](#), [Rabin 2001](#)). The EQ-5D-5L contains one item for each of five dimensions of Health Related QoL (HRQoL) (i.e., mobility, self-care, usual activities, pain or discomfort, and anxiety or depression). Response options for each item vary from having no problems (e.g., "...no problems walking about"), moderate problems (e.g., "...some problems walking about"), or extreme problems (e.g., "...unable to walk about"). Subject responses to the five dimensions of HRQoL reflect a specific health state that corresponds to a population preference weight for that state on a continuous scale of 0 (death) to 1 (perfect health). A visual analog scale (ranging from 0 to 100) is also included to capture subject's rating of their overall health status. Higher scores of the EQ-5D-5L represent better health states. All scoring and handling of data will follow the User's Guide defined by the EuroQoL Group ([Reenen 2015](#)).

7.2.5.3 Functional Assessment of Cancer Therapy–Melanoma (FACT-M)

The Functional Assessment of Cancer Therapy–Melanoma (FACT-M) quality of life questionnaire consists of the FACT-General (FACT-G) plus the Melanoma Subscale and the Melanoma Surgery Subscale, which complement the general scale with items specific to quality of life (QoL) in melanoma. Higher scores on all the FACT-M scales indicate a higher quality of life. In psychometric testing FACT-M questionnaire has been shown to be a reliable and valid instrument for subjects with melanoma that can be used for the assessment of QoL in clinical trials ([Cormier 2008](#)). For the purpose of this study the 16 items that comprise the Melanoma Subscale of the FACT-M are used.

8 Safety monitoring and reporting

8.1 Adverse events

8.1.1 Definitions and reporting

An adverse event is defined as the appearance of (or worsening of any pre-existing) undesirable sign(s), symptom(s), or medical condition(s) that occur after subject's signed informed consent has been obtained.

Subjects whose *BRAF* V600 mutation status is known will sign the main study ICF.

Abnormal laboratory values or test results occurring after informed consent constitute adverse events only if they induce clinical signs or symptoms, are considered clinically significant, require therapy (e.g., hematologic abnormality that requires transfusion or hematological stem cell support), or require changes in study medication(s).

Adverse events that begin or worsen after informed consent should be recorded in the Adverse Events eCRF. Conditions that were already present at the time of informed consent should be recorded in the Medical History page of the subject's CRF. Adverse event monitoring should be continued for at least:

- 150 days following the last dose of PDR001/placebo
- until the start of a new post-treatment antineoplastic medication if sooner than the 150 days mentioned above. If a subject starts a post-treatment antineoplastic therapy, then only adverse events suspected to be related to study treatment should be collected out to 150 days after discontinuation of PDR001/placebo.
- 30 days after the last dose of dabrafenib or 120 days after the last dose of trametinib, if the subject continued the combination partner more than 150 days after the last dose of PDR001/placebo)

Adverse events (including lab abnormalities that constitute AEs) should be described using a diagnosis whenever possible, rather than individual underlying signs and symptoms. When a clear diagnosis cannot be identified, each sign or symptom should be reported as a separate Adverse Event.

Adverse events will be assessed and graded according to the CTCAE v4.03 ([...//ctep.cancer.gov](http://ctep.cancer.gov)).

If CTCAE grading does not exist for an adverse event, the severity of mild, moderate, severe, and life-threatening, death related to the AE corresponding respectively to Grades 1 - 5, will be used. Information about any deaths (related to an Adverse Event or not) will also be collected through a Death form.

The occurrence of adverse events should be sought by non-directive questioning of the subject during the screening process after signing informed consent and at each visit during the study. Adverse events also may be detected when they are volunteered by the subject during the screening process or between visits, or through physical examination, laboratory test, or other assessments. As far as possible, each adverse event should be evaluated to determine:

1. The severity grade (CTCAE v4.03 Grade 1-5)
2. Its duration (Start and end dates)
3. Its relationship to the study treatment (Reasonable possibility that AE is related: No, Yes, investigational treatment, Yes, the study treatment (non-investigational), Yes, both and/or indistinguishable)
4. Action taken with respect to study or investigational treatment (none, dose adjusted, temporarily interrupted, permanently discontinued, unknown, not applicable)
5. Whether medication or therapy was given (no concomitant medication/non-drug therapy, concomitant medication/non-drug therapy)
6. Whether it is serious, where a serious adverse event (SAE) is defined as in [Section 8.2.1](#) and which seriousness criteria have been met

7. Outcome (not recovered/not resolved, recovered/resolved, recovering/resolving, recovered/resolved with sequelae, fatal, unknown)

If the event worsens the event should be reported a second time in the eCRF noting the start date when the event worsens in toxicity. For Grade 3 and 4 adverse events only, if improvement to a lower grade is determined a new entry for this event should be reported in the eCRF noting the start date when the event improved from having been Grade 3 or Grade 4.

For safety run-in part, any AE that constitutes a DLT should be reported like a Grade 3 and 4 adverse event.

All adverse events should be treated appropriately. If a concomitant medication or non-drug therapy is given, this action should be recorded on the Adverse Event eCRF.

Once an adverse event is detected, it should be followed until its resolution or until it is judged to be permanent, and assessment should be made at each visit (or more frequently, if necessary) of any changes in severity, the suspected relationship to the study treatment, the interventions required to treat it, and the outcome.

Progression of malignancy (including fatal outcomes), if documented by use of appropriate method (for example, as per RECIST criteria for solid tumors), should not be reported as a serious adverse event.

[figure not shown]
Adverse events separate from the progression of malignancy (example, deep vein thrombosis at the time of progression or hemoptysis concurrent with finding of disease progression) will be reported as per usual guidelines used for such events with proper attribution regarding relatedness to the drug.

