Day of cycle			-28 to -1	1	15	1	15									
CT or MRI of other metastatic sites (e.g., neck)	D	7.2.1	Following final PFS analysis; CT or MRI of other metastatic sites are no longer required. Investigators are directed to follow local procedures.													
Color Digital Photography (including a metric ruler) of skin lesions	D	7.2.1	X						Following final PFS analysis; colour digital photography of skin lesions assessments are no longer required. Investigators are directed to follow local procedures for the frequency and modality of tumor assessments.							
Body Fluid/Tissue	D	7.2.1	Needle aspiration, biopsy or any other form of collection (e.g., paracentesis, punctuation) performed for any reason													
Safety																
Adverse events	D	7.2.2, 8.1	Suspected AEs up to Day 150; non-suspected AEs up to Day 150 or start of new post treatment anti-neoplastic medication, whichever is sooner. Monitoring of new cutaneous malignancies should continue every month for 6 months following discontinuation of dabrafenib or until initiation of another antineoplastic therapy (refer to Section 6.3.5.3).													
Serious adverse events	D	8.2	Suspected SAEs up to Day 150 and beyond; non-suspected SAEs up to Day 150 or start of new post treatment anti-neoplastic medication, whichever is sooner.													

[figure not shown]
	Category	Protocol Section	Screening/Baseline	Treatment (Cycle = 28 days)						Follow-Up Period						
				Cycle 1		Cycle 2		Subsequent cycles Day 1	End of Study Treatment (EoT)	30 Day Safety Follow Up	60- Day Safety Follow Up	90- Day Safety Follow Up	120- Day Safety Follow Up	150- Day Safety Follow Up	End of Post Treatment Follow Up	Survival Follow Up
Day of cycle			-28 to -1	1	15	1	15									
Biomarkers																
Tumor tissue (archival or new) for central BRAF V600 mutation testing, assessment of IO markers and potential companion diagnostic bridging study. Note: if local BRAF V600 mutation result is not available, sample will be used for screening and should be sent for central testing by Day -20	D	7.2.4.1.1	X													

[figure not shown]
	Category	Protocol Section	Screening/Baseline	Treatment (Cycle = 28 days)						Follow-Up Period							
				Cycle 1		Cycle 2		Subsequent cycles Day 1	End of Study Treatment (EoT)	30 Day Safety Follow Up	60- Day Safety Follow Up	90- Day Safety Follow Up	120- Day Safety Follow Up	150- Day Safety Follow Up	End of Post Treatment Follow Up	Survival Follow Up	

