7.1.6 Follow up for safety evaluations

All subjects must be followed for safety up to 150 days after the last dose of PDR001/placebo. After the 30-day onsite safety follow-up visit, subjects will be followed (via telephone call or onsite visit if subject happens to be visiting the site) at 60, 90, 120 and 150 days after the last dose of PDR001/placebo ([Appendix 3](#)).

In case where individual drug components of the study treatment are discontinued at different times, subjects must be followed for safety evaluation up to 150 days following the last dose of PDR001/placebo or up to 30 days after the last dose of dabrafenib or 120 days after the last dose of trametinib, whichever is longer. In addition, subjects will be followed for skin related toxicity every month for 6 months from the last dose of dabrafenib.

All safety assessments should be completed outlined in [Section 7.1](#). However, if the subject begins post treatment antineoplastic medication before the 150-Day safety follow-up visit the collection of new SAEs and AEs unrelated to study medication will stop and thereafter only suspected AEs and suspected SAEs will continue to be collected up to Day 150. Suspected SAEs will continue to be collected beyond the 150-Day safety visit. Data collected should be added to the appropriate eCRF pages. For female subjects of child bearing potential, a pregnancy test will be performed at the time points listed in [Section 7.1](#).

Data collected should be added to the Adverse Events eCRF and the Concomitant Medications eCRF.

Following the final PFS analysis and results, safety assessments will continue per protocol schedules outlined in [Table 7-1](#), [Table 7-2](#) and [Table 7-3](#).

For subjects who transferred to Post-Trial Access (PTA), no further safety follow-ups will be performed.

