8.2.2 Reporting

For subjects with known *BRAF* V600 mutation status who sign the main study ICF, SAE collection starts at time of main study informed consent whether the subject is a screen failure or not.

To ensure subject safety, every SAE, regardless of suspected causality, occurring after the subject has provided informed consent and until at least 30 days after the subject has stopped study treatment must be reported to Novartis within 24 hours of learning of its occurrence and until

- at least 150 days following the last dose of PDR001/placebo (or all patients in a double blind study)
- 30 days after the last dose of dabrafenib or 120 days after the last dose of trametinib, if the **subject** continued the combination partner more than 150 days after the last dose of PDR001) OR

- the start of a new post-treatment antineoplastic medication if sooner than the 150 days mentioned above. If a subject starts a post-treatment antineoplastic therapy, then only SAEs suspected to be related to study treatment should be collected out to 150 days after discontinuation of PDR001/placebo. SAEs suspected to be related to PDR001/placebo will continue to be collected beyond the 150-Day safety visit.

Any additional information for the SAE including complications, progression of the initial SAE, and recurrent episodes must be reported as follow-up to the original episode within 24 hours of the investigator receiving the follow-up information. An SAE occurring at a different time interval or otherwise considered completely unrelated to a previously reported one should be reported separately as a new event.

Any SAEs experienced after the reporting period described above should only be reported to Novartis if the investigator suspects a causal relationship to the study treatment.

Information about all SAEs is collected and recorded on the Serious Adverse Event Report Form; all applicable sections of the form must be completed in order to provide a clinically thorough report. The investigator must assess and record the relationship of each SAE to each specific study treatment (if there is more than one study treatment), complete the SAE Report Form in English, and submit the completed form within 24 hours to Novartis. Detailed instructions regarding the SAE submission process and requirements for signatures are to be found in the investigator folder provided to each site

[figure not shown]

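### Sections 8.1.1 and 8.2.2 put a 150-day condition on the dabrafenib and trametinib AE/SAE windows that Section 7.1.6 does not, so required collection can end up to 120 days early (90 for non-suspected SAEs)

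*Protocol*

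**What the plan says.** **Section 7.1.6.** If components stop at different times, subjects must be followed to 150 days after PDR001/placebo, or "up to 30 days after the last dose of dabrafenib or 120 days after the last dose of trametinib, whichever is longer". No minimum duration of partner dosing is set. After the 30-day visit, the scheduled safety contacts are "at 60, 90, 120 and 150 days after the last dose of PDR001/placebo"; none is tied to the last partner dose, apart from monthly skin follow-up for six months after dabrafenib.

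**Section 8.1.1 (AEs).** "Adverse event monitoring should be continued for at least" 150 days after PDR001/placebo. The dabrafenib and trametinib windows are listed too, but only "if the subject continued the combination partner more than 150 days after the last dose of PDR001/placebo".

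**Section 8.2.2 (SAEs).** The same condition appears: the partner windows count if the subject "continued the combination partner more than 150 days after the last dose of PDR001) OR". The lead sentence adds a floor: every SAE "until at least 30 days after the subject has stopped study treatment must be reported to Novartis". After the reporting period, SAEs "should only be reported to Novartis if the investigator suspects a causal relationship to the study treatment".

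**Tables 7-1 to 7-3.** The AE row reads "Suspected AEs up to Day 150; non-suspected AEs up to Day 150 or start of new post treatment anti-neoplastic medication". The SAE row likewise ends non-suspected SAEs at Day 150 and lets suspected SAEs run on. The only partner-based clause is the monthly check for new cutaneous malignancies after dabrafenib.

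**The concern.** Three parts of the protocol tell a site when to stop collecting safety data, and they give different days for the same subject. The condition tests how long the partner was dosed, whereas what matters is whether the partner's own risk window runs past day 150. This produces a cliff: with trametinib stopped on day 150 after PDR001/placebo the 8.1.1 minimum ends that same day, and with trametinib stopped on day 151 it ends on day 271.

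Staggered stopping is foreseeable. Under Section 8.3, placebo infusions cease after the final PFS analysis and continuation of PDR001 is decided case by case, while the study stays open to gather further survival and safety data. At stake are non-serious AEs and non-suspected SAEs in the weeks after the last trametinib or dabrafenib dose, which are collected or not according to the page a site follows.

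**Working it through.** No stated figure needs reproducing. The check turns each rule into a last collection day.

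**Inputs.** Day 0 is the last PDR001/placebo dose, *b* the last dabrafenib day and *t* the last trametinib day. The windows of 150, 30 and 120 days come from 7.1.6, 8.1.1 and 8.2.2; the 30-day SAE floor comes from 8.2.2. Day 150 in the tables is taken as 150 days after PDR001/placebo, the anchor used in 7.1.6.

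**Rules.**
- 7.1.6: end = max(150, b+30, t+120).
- 8.1.1: end = 150 if b and t are both at most 150. A partner dosed beyond day 150 adds its own window.
- 8.2.2, non-suspected SAEs: as 8.1.1, but never before the last dose of any drug + 30.

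**Shortfall when b and t are both at most 150.**
- AEs: max(150, b+30, t+120) − 150.
- Non-suspected SAEs: max(150, b+30, t+120) − max(150, b+30, t+30).

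| t | b | 7.1.6 end | 8.1.1 end | AE gap | 8.2.2 end | SAE gap |
|---|---|---|---|---|---|---|
| 31 | 31 | 151 | 150 | 1 | 150 | 1 |
| 60 | 60 | 180 | 150 | 30 | 150 | 30 |
| 90 | 90 | 210 | 150 | 60 | 150 | 60 |
| 120 | 120 | 240 | 150 | 90 | 150 | 90 |
| 150 | 150 | 270 | 150 | 120 | 180 | 90 |
| 151 | 151 | 271 | 271 | 0 | 271 | 0 |
| 100 | 150 | 220 | 150 | 70 | 180 | 40 |
| 0 | 121 | 151 | 150 | 1 | 151 | 0 |
| 0 | 150 | 180 | 150 | 30 | 180 | 0 |

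The maximum is 120 days for AEs and 90 days for non-suspected SAEs. The 30-day floor removes any SAE gap arising from dabrafenib alone.

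**Dabrafenib beyond day 150.**
- t = 31, b = 160: 7.1.6 gives max(150, 190, 151) = 190 and 8.1.1 gives 190, so the gap is 0.
- t = 100, b = 170: 7.1.6 gives 220. 8.1.1 gives 200 if the condition is read drug by drug (gap 20), or 220 if one partner past day 150 triggers both windows (gap 0).

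**Reach into the analyses.** Section 10.5.3.1 closes the on-treatment period 30 days after the last dose of any study drug, and Section 10.5.3.2 builds the AE summary tables on that period. The additional summaries in 10.5.3.1 stop 150 days after PDR001/placebo. With L = max(b, t) at most 150, the on-treatment period passes day 150 only if L is at least 121, and by L + 30 − 150 = L − 120 days: 1 day at L = 121, 30 days at L = 150. An EOT visit at the latest permitted day, 157, reduces the 30 to 180 − 157 = 23. The same visit reduces the largest AE gap from 120 to 270 − 157 = 113.

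**The case against.** The strongest reply is that 8.1.1 states a minimum, so a site that follows 7.1.6 satisfies both sections. That is right, and a reader who infers that the sections cannot both be obeyed goes too far. It does not remove the problem. The table rows give Day 150 as an end, 7.1.6 itself sends sites to Section 7.1 for the safety assessments, and 8.2.2 restricts later SAE reports to suspected ones.

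A second reply is that existing safeguards already cover much of the gap. On-treatment visits continue every four weeks, the EOT visit falls within 7 days of the last dose, detected AEs are followed to resolution, and new antineoplastic therapy ends collection of unrelated events anyway. Monthly short examinations run for six months after dabrafenib. Taking six months as 180 days, they reach t + 120 only if dabrafenib stopped no more than 60 days before trametinib, and they cover general appearance, skin, blood pressure and pulse. All this narrows the loss without closing it.

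Three stronger readings are tempting and unsupported:
- **That 120 days drop out of the AE tables.** Beyond both day 150 and 30 days after the last dose, an AE enters listings only.
- **That serious drug reactions go unreported.** Suspected SAEs have no time limit.
- **That AE ascertainment differs between arms.** Stopping placebo makes this conceivable, but the protocol gives no count of affected subjects in either arm.

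**Conclusion.** The inconsistency stands. When both partners stop by day 150 after PDR001/placebo, the 8.1.1 minimum ends up to 120 days before 7.1.6 requires, and the 8.2.2 period for non-suspected SAEs up to 90 days before. If dabrafenib continues past day 150 the shortfall shrinks or disappears, so the figures do not apply to every subject whose trametinib stops on days 31 to 150.

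The consequence for analysis is small: at most 30 days of treatment-emergent AE collection, for a last partner dose on days 121 to 150. The remainder matters for listings and for surveillance within the protocol's own trametinib window. PFS, OS, alpha and power are unaffected.

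The conclusion assumes that Day 150 in the tables counts from PDR001/placebo. The content of the Appendix 3 flow chart and the protocol text preceding these schedules were not available to check. The number of affected subjects is unknown.

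**What to change.** 1. Delete the more-than-150-days condition in 8.1.1 and 8.2.2 and use the longest-window rule of 7.1.6. All three sections then give the same end day; with both partners stopped on day 150, that is day 270.
2. Align the AE and SAE rows of Tables 7-1 to 7-3 with that rule.
3. Add a telephone safety contact at the end of the partner window (30 days after dabrafenib or 120 days after trametinib) when this falls after day 150. Without it the longer window has no contact of its own, because the scheduled calls end 150 days after PDR001/placebo.

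The cost is a wording change in two sections and three tables, somewhat longer AE collection, and one or a few extra calls for the affected subjects.
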